As of 03-Feb-2022, 1840 patients have been screened and 1382 patients have been randomized and treated in the CANOPY A trial. On 23-Apr-2021, the interim analysis of DFS related to futility was performed by independent Data Monitoring Committee (DMC) when 201 DFS events were documented on 01-Feb-2021. The trial was recommended to continue without modification. The last independent DMC review of the safety data from 1234 randomized patients (cut-off date 01-Sep-2021), and the serious adverse events (cut-off date 21-Nov-2021) took place on 12-Dec-2021. The DMC recommendation was that the study can continue without modifications.

The main purpose of this protocol amendment is to:

- Remove the second interim analysis for Disease Free Survival (DFS) originally planned
- Include the comparison between the canakinumab and placebo arms of DFS by investigator local assessment and OS in subgroups defined respectively by PD-L1 and CD8 expression as secondary endpoint.
- Add time to first 10 point deterioration for symptoms and global health status/QoL as a secondary patient-reported outcomes variable of interest
- Add disruption proofing language

Rationale for updating the interim analysis plan for DFS

The originally planned 2nd interim analysis of DFS in this event-driven trial was not performed since the pre-specified number of DFS for this interim analysis (294) had been reached before the planned 1500 subjects were randomized and did not have at least one post-baseline efficacy assessment, which is required by the protocol. As such all the relevant wording in section 4 and 10 are not applicable anymore and have been removed.

As per protocol, the final DFS analysis is planned to be performed when approximately 392 progression events have been observed and all enrolled subjects have a minimal efficacy followup of 3 months to ensure all subjects have at least one post-baseline recurrence assessment.

Per sponsor's decision, considering the projected number of DFS events approaching the target for the final DFS analysis the screening activities ended on December 7th, 2021. A total of 1382 subjects were randomized, which is less than 1500 subjects originally planned.

Rationale for including PD-L1 subgroup analysis as a secondary endpoint

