- Section 10.9: Clarified the power calculation to align with the updated number of analyses for OS
- Section 11.3: as part of the latest protocol template, it has been added that ICF may be collected remotely. Updated ICH GCP to ICH E6 GCP for consistency throughout protocol.
- Section 11.5: Clarified that any data analysis carried out independently by the Investigator should be submitted to Novartis before publication or presentation. Additionally, summary results of primary and secondary endpoints will be disclosed based upon the global Last Patient Last Visit (LPLV) date, since multinational studies are locked and reported based upon the global LPLV.
- Section 13: New references added
- Appendix 2: addition of stage group IV.

The protocol summary has been updated to reflect the changes throughout the document as well as the list of abbreviations and glossary of terms.

Editorial revisions and text corrections were also included throughout the document.

IRBs/IECs

A copy of this amended protocol will be sent to the Institutional Review Board (IRBs)/Independent Ethics Committee (IECs) and Health Authorities.

The changes described in this amended protocol require IRB/IEC approval prior to implementation.

The changes herein affect the Informed Consent. Sites are required to update and submit for approval a revised Informed Consent that takes into account the changes described in this protocol amendment.

Amendment 02 (05-Feb-2020)

Amendment rationale

As of 05-Feb-2020, 742 patients have been screened and 507 patients have been randomized and treated.

The purpose of the protocol amendment is to allow local laboratory hematology, chemistry, and coagulation to be performed for scheduled safety monitoring visits. Canakinumab has a well-defined safety profile, as outlined in the canakinumab Investigator's Brochure (current Edition 18). Allowing sites the flexibility to perform hematology, chemistry, and coagulation based on local laboratory results allows for same-day safety evaluations. The remaining blood specimens collected as part of safety monitoring (e.g., HIV screen, HbsAg, HCV antibody) will continue to be performed by central laboratory.

Rationale for lipase and amylase grade 2, 3, and 4 update: Definition of grades 2, 3, and 4 lipase and amylase are updated in the dose modification table based on CTCAE v 5.0.

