The primary endpoint was not met for this study as described in the [[CACZ885T2301 Primary Analysis CSR](#)]; therefore, no formal statistical analysis will be performed for this close-out CSR. The outputs for the close-out CSR consist mainly of summary tables prepared using descriptive statistics as well as data listings.

2 Planned tables, figures and listings

The table below provides the list of outputs that need to be generated, with additional guidelines added under 'Notes'. Please follow the in-text layout given below, post-text output has been added for reference.

Add footnote: CACZ885T2301- *Cut-off date*: 07Feb2023

Output Number in close-out CSR	Output title in close-out CSR	Output number in primary CSR	Output title in primary CSR	Notes
Table 2-1	Subject disposition (Full analysis set)	Table 10-1	Subject disposition (Full analysis set)	
Table 2-2	Protocol deviation ($\geq 0.4\%$ for any treatment arm) (Full analysis set)	Table 10-2	Protocol deviation ($\geq 0.4\%$ for any treatment arm) (Full analysis set)	
Table 2-3	Duration of exposure to study drug (Safety set)	Table 10-7	Duration of exposure to study drug (Safety set)	
Table 2-4	Dose of study drug received (Safety set)	Table 10-8	Dose of study drug received (Safety set)	
Table 2-5	Dose interruptions and discontinuation of study drug (Safety set)	Table 10-9	Dose interruptions and discontinuation of study drug (Safety set)	
Table 2-6	Summary of overall survival by study arm (Full analysis set)	Table 11-3	Summary of overall survival by study arm (Full analysis set)	

Table 2-6a	Summary of overall survival by study arm and baseline PD-L1 subgroup (Baseline PD-L1: < 1% vs. ≥ 1%) (Full analysis set)	Table 11-3a	Summary of overall survival by study arm and baseline PD-L1 subgroup (Baseline PD-L1: < 1% vs. ≥ 1%) (Full analysis set)	
Table 2-6b	Summary of overall survival by study arm and baseline PD-L1 subgroup (Baseline PD-L1: < 1% vs. ≥ 1% and < 49% vs. ≥ 50%) (Full analysis set)	Table 11-3b	Summary of overall survival by study arm and baseline PD-L1 subgroup (Baseline PD-L1: < 1% vs. ≥ 1% and < 49% vs. ≥ 50%) (Full analysis set)	
Table 2-6c	Summary of overall survival by study arm and baseline PD-L1 subgroup (Baseline PD-L1: < 50 % vs. ≥ 50%) (Full analysis set)	Table 11-3c	Summary of overall survival by study arm and baseline PD-L1 subgroup (Baseline PD-L1: < 50 % vs. ≥ 50%) (Full analysis set)	

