This statistical analysis plan (SAP) describes all planned analyses for the primary Clinical Study Report (CSR) of study CACZ885T2301, a phase III, multicenter, randomized, double blind, placebo-controlled study evaluating the efficacy and safety of canakinumab versus placebo as adjuvant therapy in adult subjects with stages AJCC/UICC v8 II-III A and IIIB (T>5cm N2) completely resected (R0) non-small cell lung cancer (NSCLC). As specified in Section 4.3 of the study protocol version 03 (dated 03-Feb-2022), the final analysis of DFS will occur when approximately 392 DFS events are reached and the primary CSR will be based on the final DFS analysis.

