2.5.4 Supportive analyses for primary estimand

2.5.4.1 Sensitivity analyses for primary estimand

First sensitivity analysis estimand: The target population, the primary variable, the treatment of interest, intercurrent events, and the summary measure of this endpoint are the same as those for the primary estimand. To assess the impact of stratification, the two treatment arms will be compared using the unstratified log-rank test. In the summary tables, this approach is referred to as '*unstratified DFS sensitivity analysis*'.

Second sensitivity analysis estimand: the target population, the primary variable, the treatment of interest, intercurrent events, and the summary measure of this endpoint are the same as those for the primary estimand. The two treatment arms will be compared using the stratified log-rank test with stratification factors derived from the clinical database. In the summary tables, this approach is referred to as '*DFS sensitivity analysis with stratification factors from eCRF*'.

Third sensitivity analysis estimand: the target population, the primary variable, the treatment of interest, intercurrent events, and the summary measure of this endpoint are the same as those for the primary estimand. Subjects with two or more times missing tumor assessments will be censored at the last adequate tumor assessment. Algorithm to identify missing tumor assessments are defined in [Appendix 5.6](#). In the summary tables, this approach is referred to as ‘*DFS sensitivity analysis with censoring for two or more missing assessments*’.

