5.6 Missing tumor assessments

The term ‘missing adequate tumor assessment’ is defined as a tumor assessment not done. For the sake of simplicity, a ‘tumor assessment’ will be referred to as an ‘assessment’ and a ‘missing adequate tumor assessment’ will be referred to as a ‘missing assessment’.

The presence and the number of missing assessments affects DFS censoring and event date.

An exact rule to determine whether there is no, one or two missing assessments is therefore needed. This rule is based:

- on the duration between LATA date and the event date
- on the duration between LATA date and the cut-off date

In this study, the protocol defined schedule of assessments is

- every 12 weeks during the first year (i.e. at weeks 12, 24, 36 and 48),
- every 26 weeks through year 2 and year 3 (i.e. at weeks 74, 100, 126 and 152),
- every 52 weeks through year 4 and year 5 (i.e. at weeks 204 and 256).

The scheduled date of assessments (in weeks from randomization), protocol specified windows for assessment, and the thresholds for LARA to belong to a visit can be found in [Table 5-3](#).

Table 5-3 Schedule for assessments, time windows and D1/D2 (weeks)

assessment schedule		Scheduled date – one week*	Schedule date (weeks from randomization)	Scheduled date + one week*	Threshold (weeks)**	Boundary of assessment*** (start, end]	D1/D2****
Every 12 weeks for the first year	1 st (C5D1)	11	12	13	18	(0,18]	14/26
	2 nd (C9D1)	23	24	25	30	(18,30]	14/26
	3 rd (C13D1)	35	36	37	42	(30,42]	14/40
	4 th (C17D1)	47	48	49	61	(42,61]	28/54
Every 26 weeks for the second and third year	5 th	73	74	75	87	(61,87]	28/54
	6 th	99	100	101	113	(87,113]	28/54
	7 th	125	126	127	139	(113,139]	28/80
	8 th	151	152	153	178	(139,178]	54/106
Every 52 weeks for the four and fifth year	9 th	203	204	205	230	(178,230]	54/106
	10 th	255	256	257	282	(230, 282]	54/106

* These start and end study weeks are used to determine if a visit is on schedule. For example, a visit between study week 23 and study week 25 is considered the 2nd ‘on schedule’ assessment.

** The threshold correspond to the mid-point between current and next visit and to the upper limit for LARA to be matched to a certain scheduled assessment e.g. if LARA is at week 45, this is after the threshold for 3rd recurrence assessment (C13D1) and before that for the 4th recurrence assessment, so the matching schedule assessment is the 4th recurrence assessment (C17D1).

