*** These boundaries are defined according to assessment thresholds to calculate D1 and D2. For example: (30, 42] means any assessment falls into this time interval will be considered as the 3rd assessment visit.

**** D1 and D2 are defined per the protocol-specified recurrence assessment schedule

- The threshold D1 is defined as the protocol-specified time interval between the assessments plus 2x the protocol-allowed time window around the assessments (i.e. = 2*1 week=2 weeks).
- The threshold D2 is defined as twice the protocol-specified time interval between the assessments plus 2x the protocol-allowed time window around the assessments

Since there are changes in schedule for assessments during the 5 year tumor assessment period, D1 and D2 are defined differently depending on when LATA occurs. Here are the rules based on when LATA occurs:

- **Rule 1:** if LATA happens within 30 weeks after randomization (\leq study day 210 day), the applicable scheduled tumor assessments are the 1st and 2nd assessment (on C5D1 and C9D1), $D1 = 12 + 2 = 14$ weeks and $D2 = 12 * 2 + 2 = 26$ weeks.
- **Rule 2:** if LATA happens after 30 weeks but within 42 weeks, the matched scheduled tumor assessment is 3rd assessment (on C13D1), the study period: \geq study day 211 and \leq study day 294, $D1 = 12 + 2 = 14$ weeks and $D2 = 12 + 26 + 2 = 40$ weeks.
- **Rule 3:** if LATA happens after 42 weeks but within 113 weeks, the applicable scheduled tumor assessments are 4th, 5th and 6th assessments, the study period: \geq study day 295 and \leq study day 791, $D1 = 26 + 2 = 28$ weeks and $D2 = 26 * 2 + 2 = 54$ weeks.
- **Rule 4:** if LATA happens after 113 weeks but within 139 weeks, the matched scheduled tumor assessment is 7th assessment, the study period: ≥ 792 days and ≤ 973 days, $D1 = 26 + 2 = 28$ weeks and $D2 = 26 + 52 + 2 = 80$ weeks.
- **Rule 5:** if LATA happens after 139 weeks, the applicable scheduled tumor assessments are 8th, 9th and 10th assessments, the study period: ≥ 974 days, $D1 = 52 + 2 = 54$ weeks and $D2 = 52 * 2 + 2 = 106$ weeks.

The number of missing events is defined as:

- An event after LATA+D1 weeks will be considered as having ≥ 1 missing assessment
- An event after LATA+D2 weeks will be considered as having ≥ 2 missing assessments

6 Reference

1. Brookmeyer R and Crowley J (1982). A Confidence Interval for the Median Survival Time. *Biometrics*, 38, 29 - 41.

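### SAP 5.6 sets the missed-scan thresholds D1/D2 with a 1-week window where protocol version 03 allows 2 and 3 weeks: a minor inconsistency touching one DFS sensitivity analysis (about 0 to 0.6 events)

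*SAP*

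**What the plan says.** SAP 5.6 decides from the time since the last adequate tumor assessment (LATA) whether scans were missed. D1 is one scheduled interval, and D2 two, plus "2x the protocol-allowed time window around the assessments (i.e. = 2*1 week=2 weeks". The resulting D1/D2 pairs, in weeks, are 14/26 for scheduled scans 1-2, 14/40 for scan 3, 28/54 for scans 4-6, 28/80 for scan 7 and 54/106 for scans 8-10. The rule is then "An event after LATA+D2 weeks will be considered as having" two or more missing assessments. The on-schedule columns of Table 5-3 also use one week either side; the footnote's example is that "a visit between study week 23 and study week 25 is considered the 2nd" on-schedule scan.

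D2 is applied in the third sensitivity analysis of SAP 2.5.4.1: "Subjects with two or more times missing tumor assessments will be censored at the last adequate tumor assessment".

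The SAP names the protocol version it follows: "As specified in Section 4.3 of the study protocol version 03 (dated 03-Feb-2022"). In that version, Sections 7.1, 7.1.3 and 7.2.1 agree that imaging may be done within 14 days of the due date in years 1-3 and within 21 days in years 4-5. The amendment logs date these windows. The years 1-3 window was 7 days until Amendment 03 (03-Feb-2022), and the years 4-5 window has been 21 days since Amendment 02 (05-Feb-2020).

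**The concern.** The definition refers to the window the protocol allows, but the number entered is not that window in any year of the current protocol. A programmer working from the definition and one working from the table would get different thresholds.

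The SAP document history suggests an oversight. The D1/D2 method entered on 10-Mar-2021, and the 21-Mar-2022 entry, which brings the SAP into line with Amendment 03, does not mention Section 5.6. The years 4-5 constants were already out of step in 2021.

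What is at stake is narrow. If D2 is too short, a recurrence found by a patient who missed one scan, and whose neighbouring scans were both in window, is treated as if two had been missed. A real event is then censored in the analysis meant to test robustness to missed scans.

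**Working it through.** **Inputs.** Scan weeks 12, 24, 36, 48, 74, 100, 126, 152, 204, 256 (SAP 5.6). Windows of 2 weeks for scans 1-8 and 3 weeks for scans 9-10 (protocol 7.2.1). 392 planned DFS events (protocol 10.8).

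**The plan's own figures.** D1 = weeks to the next scan + 2, and D2 = weeks to the next scan but one + 2, reproduce all ten pairs in Table 5-3 (continuing the 52-week interval past week 256 for the last rows).

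**Gap after exactly one missed scan.** The largest in-window gap is the nominal gap + window of the last scan + window of the event scan. The shortest in-window gap after two missed scans is that longer nominal gap minus the two windows. All values are in weeks.

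| LATA at scan | Nominal gap, one missed | SAP D2 | Largest gap, one missed | Shortest gap, two missed (current windows) | Same, years 1-3 at 7 days |
|---|---|---|---|---|---|
| 1 | 24 | 26 | 28 | 32 | 34 |
| 2 | 24 | 26 | 28 | 46 | 48 |
| 3 | 38 | 40 | 42 | 60 | 62 |
| 4 | 52 | 54 | 56 | 74 | 76 |
| 5 | 52 | 54 | 56 | 74 | 76 |
| 6 | 52 | 54 | 56 | 99 | 100 |
| 7 | 78 | 80 | 83 | 125 | 126 |
| 8 | 104 | 106 | 109 | none scheduled | none scheduled |

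Example: last scan at week 10 (12 - 2), week-24 scan missed, recurrence seen at week 38 (36 + 2). The gap is 28 weeks, above D2 = 26, so Rule 1 counts at least two missed scans although only one was.

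**Chance of misclassification.** D2 exceeds the nominal gap by 2 weeks in every row, so the error needs the two scans to drift apart by more than 2 weeks in total. With scan dates uniform in their windows, this has probability 0 if both windows are 1 week, 1/16 = 0.0625 if the first is 1 week and the second 2, and 1/8 = 0.125 if both are 2.

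**Exposed events.** The Amendment 03 rationale says that "the pre-specified number of DFS for this interim analysis (294) had been reached before the planned 1500 subjects were randomized". At most 392 - 294 = 98 events therefore came later. If 5-10% of them follow exactly one missed scan (an assumption; the documents give no rate), and the wider window applies only to the event scan:

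- 98 x 0.05 x 0.0625 = 0.31
- 98 x 0.10 x 0.0625 = 0.61

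This overstates the number. The 98 include deaths and recurrences on unscheduled scans, and the wider window could not be used at once: "The changes described in this amended protocol require IRB/IEC approval prior to implementation".

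**Rows 7 and 8.** The close-out SAP gives a late bound on scan dates: "Add footnote: CACZ885T2301- *Cut-off date*: 07Feb2023". A gap above D2 by then needs randomization before about 05-Mar-2019 for row 7 (125 + 80 = 205 weeks earlier) or 06-Mar-2018 for row 8 (151 + 106 = 257 weeks earlier). Only 63 subjects had been randomized by 11-Dec-2018, so these rows add almost nothing.

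**Weight of one event.** With 392 events split equally, one event removed from one arm shifts the log hazard ratio by about ln(196/195) = 0.005, against a standard error of 2/sqrt(392) = 0.10.

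**The case against.** The best defence is that one week was the right value for most of the data. Years 1-3 scans were held to 7 days until seven weeks before this SAP was released, and at least 294 of the 392 events belong to that period, when in-window scans could not be misclassified. The rule is also explicit enough to program, and it serves one sensitivity analysis. This stands as an argument about size. It does not reconcile the constants with the definition or with the protocol version the SAP cites.

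A second objection is that larger thresholds create the opposite error. This also stands in part. Take a last scan at week 14, the week-24 and week-36 scans both missed (their windows close at weeks 26 and 38), and death at week 41. The gap is 27 weeks: D2 = 26 correctly counts two missed scans, and D2 = 28 does not. The same happens under 7-day windows with a last scan at week 13 and death at week 40. For scheduled in-window scans the problem cannot arise, because the shortest double-miss gap exceeds the corrected D2 in every row from 1 to 7.

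A reader might also infer three stronger things that the documents do not support:

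- **The primary analysis is affected.** SAP 5.6 does say that missing assessments influence DFS censoring. But SAP Table 2-5, which governs primary censoring, uses neither D1 nor D2, and D1 triggers no censoring in any listed analysis.
- **The 2-week window applied throughout.** That would give roughly 1 to 4 events (392 x 0.85 x 0.02 to 0.10 x 0.125 = 0.8 to 4.2, assuming 85% of events are scan-detected recurrences). The amendment history rules it out.
- **Both scans bounding the gap fell after Amendment 03.** That would double the estimate to 98 x 0.05 to 0.10 x 0.125 = 0.6 to 1.2. It needs an event no earlier than 03-Feb-2022 + 26 weeks = 04-Aug-2022, and nothing in the documents places such an event before the primary DFS cut-off, whose date is not given.

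**Conclusion.** This is a minor consistency error, but the rule is wrong as written. D2 is 2 weeks short of the largest in-window gap for scans 1-6 and 3 weeks short for scans 7-8. The consequence is confined to the third DFS sensitivity analysis, where about 0 to 0.6 events would be wrongly censored. That is an upper range, resting on two assumptions from outside the documents: 5-10% of events follow exactly one missed scan, and scan dates are uniform within their window. An error of this size would not change how that analysis is read. The case for correcting it is that the SAP should agree with itself and with the protocol, and that doing so is cheap.

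**What to change.** Define D1 and D2 as the scheduled interval(s) plus the sum of the windows of the scans at the two ends of the gap; twice the window has no single value where the window changes. Then restate Table 5-3 and Rules 1-5 (D1/D2 in weeks):

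- scans 1-2: 16/28
- scan 3: 16/42
- scans 4-6: 30/56
- scan 7: 30/83
- scan 8: 57/109
- scan 9: D1 = 52 + 3 + 3 = 58

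D2 for scans 9-10 has no effect, because no scan is scheduled two visits later. Rule 5 now gives scans 8-10 one pair, so split it and give scan 8 its own. Align the on-schedule columns to 2 weeks (years 1-3) and 3 weeks (years 4-5); they drive no listed calculation.

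State the trade-off in the SAP: for deaths and unscheduled recurrences the later cut-off can occasionally count two truly missed scans as one, so a few such events would be kept rather than censored in this analysis.

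The cost is one definition sentence, the table and rule numbers, one split rule and the program constants. No new data are needed.
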